### **2.3. Benefit/Risk Assessment**

This trial is designed primarily to evaluate the efficacy, safety, and tolerability of darigabat 25 mg BID in the target patient population.

There are no identified risks for darigabat at this time. Somnolence and dizziness, fetal toxicity, bone marrow suppression, impairment of spermatogenesis and on male fertility, and increased mitoses are considered potential risks; however, these potential risks will be minimized during the trial by monitoring AEs, monitoring cell blood counts, and requiring the use of appropriate contraception and regular pregnancy testing.

Based on available safety data for darigabat, the proposed dose of 25 mg darigabat BID is considered to be safe.

More detailed information regarding benefit/risk assessment for darigabat is available in the Investigator's Brochure.

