3.2.1.1. Adverse Event of Special Interest

AESIs are defined as any event meeting the following criteria:

- AEs that result in the discontinuation of IMP
- AEs potentially related to abuse (refer to the Abuse Potential Monitoring Plan [APMP] document for details)
- AEs of suicidality
- C-SSRS (Since Last Visit) “Yes” answer to Suicidal Ideation Items #4 or #5 or any Suicidal Behaviors
- Corrected QT values using Fridericia's method (QTcF) >500 ms or an increase >60 ms from Baseline
- Liver enzymes:
 - ALT or AST $\geq 3 \times$ Upper Limit of Normal (ULN) and serum bilirubin $\geq 2 \times$ ULN (suspected Hy's Law)
 - ALT $\geq 5 \times$ ULN
- Hematologic abnormalities:
 - Absolute neutrophil count $< 1.5 \times 10^9/L$
 - Platelet count $< 100 \times 10^9/L$
 - Hemoglobin < 10 g/dL

These events will be noted by the investigator in the ADVERSE EVENT/ADVERSE EVENT OF SPECIAL INTEREST eCRF.

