3.2.2.1. Treatment-Emergent Laboratory Abnormality and Toxicity

A treatment-emergent laboratory abnormality is defined as value outside the normal range which occurs on or after the start of IMP and through the last follow up contact.

A treatment-emergent laboratory toxicity is defined as an increase of at least one toxicity grade ([Section 9.5](#)) from the baseline assessment at any post baseline visit which occurs after the first administration of IMP and through last follow up contact. If a laboratory assessment obtained on Day 1 has unknown collection times, it will be assumed to be an assessment prior to the initiation of IMP. If the relevant baseline assessments are missing for a given participant, then any post-baseline graded toxicity (i.e., at least Grade 1) is considered a treatment-emergent laboratory toxicity.

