5.17.3. Clinical Laboratory Assessments

Descriptive summaries of selective (quantitative) clinical laboratory results and change from baseline will be presented by study visit.

Additionally, for hematology, blood chemistry, coagulation, and urinalysis parameters, toxicity grade will be determined for laboratory tests with toxicity grade specified in [Section 9.5](#). Shifts from baseline to greatest (worst) post-baseline laboratory grade will be presented. For parameters not graded as described above, laboratory values outside the normal range for each systematically collected hematology, blood chemistry, and urinalysis parameters defined in Protocol Section 10.2 will be identified using shift tables. Each subject's hematology, blood chemistry, and quantitative urinalysis values will be flagged as "low" (below the lower limit of normal/LLN), "normal" (within the normal range), or "high" (above the upper limit of normal/ULN) relative to the normal ranges of the central laboratory. Each subject's qualitative urinalysis values will be flagged as "normal" or "abnormal". Shifts from baseline to high/normal/low status for the hematology, blood chemistry, and urinalysis parameters will be presented to for the maximum post-baseline value and the minimum post-baseline value for each laboratory test. Shifts from baseline to normal/abnormal status for urinalysis parameters will be presented to the maximum post-baseline value and the minimum post-baseline value for each laboratory test.

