- Grade 2 from 0.9 to <1.2 mg/dL,
- Grade 3 from 0.7 to <0.9 mg/dL,
- Grade 4 <0.7 mg/dL

Lab Test = Potassium

CTCAE Term	Grade 1	Grade 2	Grade 3	Grade 4	Grade 5
Hyperkalemia	>ULN - 5.5 mmol/L	>5.5 - 6.0 mmol/L; intervention initiated	>6.0 - 7.0 mmol/L; hospitalization indicated	>7.0 mmol/L; life- threatening consequences	Death
Hypokalemia	<LLN - 3.0 mmol/L	Symptomatic with <LLN - 3.0 mmol/L; intervention indicated	<3.0 - 2.5 mmol/L; hospitalization indicated	<2.5 mmol/L; life- threatening consequences	Death

Hyperkalemia will have grades 1-4,

- Grade 1 being any values from the ULN to 5.5 mmol/L,
- Grade 2 from >5.5 to 6.0 mmol/L,
- Grade 3 from >6.0 to 7.0 mmol/L,
- Grade 4 from >7.0 mmol/L

Hypokalemia will have grades 1, 3, and 4,

- Grade 1 being any values from the LLN to 3.0 mmol/L,
- Grade 3 from >2.5 to 3.0 mmol/L,
- Grade 4 <2.5 mmol/L

Lab Test = Sodium

CTCAE Term	Grade 1	Grade 2	Grade 3	Grade 4	Grade 5
Hypernatremia	>ULN - 150 mmol/L	>150 - 155 mmol/L; intervention initiated	>155 - 160 mmol/L; hospitalization indicated	>160 mmol/L; life- threatening consequences	Death
Hyponatremia	<LLN - 130 mmol/L	125-129 mmol/L and asymptomatic	125-129 mmol/L symptomatic; 120-124 mmol/L regardless of symptoms	<120 mmol/L; life- threatening consequences	Death

Hypernatremia will have grades 1-4,

- Grade 1 being any values from the ULN to 150 mmol/L,
- Grade 2 from >150 to 155 mmol/L,
- Grade 3 from >155 to 160 mmol/L,
- Grade 4 from >160 mmol/L

Hyponatremia will have grades 1-4,

- Grade 1 being any values from the LLN to 130 mmol/L,
- Grade 2 from 125 to <130 mmol/L,
- Grade 3 from 120 to <125 mmol/L,
- Grade 4 <120 mmol/L

Lab Test = Triglycerides

CTCAE Term	Grade 1	Grade 2	Grade 3	Grade 4	Grade 5
Hypertriglyceridemia	150 mg/dL - 300 mg/dL; 1.71 mmol/L - 3.42 mmol/L	>300 mg/dL - 500 mg/dL; >3.42 mmol/L - 5.7 mmol/L	>500 mg/dL - 1000 mg/dL; >5.7 mmol/L - 11.4 mmol/L	>1000 mg/dL; >11.4 mmol/L; life-threatening consequences	Death

Triglycerides will have grades 1-4,

- Grade 1 being any values from the 150 to 300 mg/dL,
- Grade 2 from >300 to 500 mg/dL,
- Grade 3 from >500 to 1000 mg/dL,
- Grade 4 from >1000 mmol/L

Lab Test = Uric Acid

CTCAE Term	Grade 1	Grade 2	Grade 3	Grade 4	Grade 5
Hyperuricemia	>ULN without physiologic consequences	-	>ULN with physiologic consequences	Life-threatening consequences	Death

Uric Acid will not be CTCAE graded.

Lab Test = Bicarbonate or CO2

CTCAE Term	Grade 1	Grade 2	Grade 3	Grade 4	Grade 5

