Anemia	Hemoglobin (Hgb) <LLN - 10.0 g/dL; <LLN - 6.2 mmol/L; <LLN - 100 g/L	Hgb <10.0 - 8.0 g/dL; <6.2 - 4.9 mmol/L; <100 - 80g/L	Hgb <8.0 g/dL; <4.9 mmol/L; <80 g/L; transfusion indicated	Life-threatening consequences; urgent intervention indicated	Death
Hemoglobin Increased	Increase in > 0-2	Increase in >2-4g/dL	Increase > 4 g/DL	-	Death

Decreased Hemoglobin will have grades 1-3, with

- Grade 1 being any values from the LLN to 10 g/DL,
- Grade 2 from 8 to < 10 g/DL and
- Grade 3 < 8 g/DL

Increased Hemoglobin will not be graded.

Lab Test = CD4 Lymphocytes

CTCAE Term	Grade 1	Grade 2	Grade 3	Grade 4	Grade 5
CD4 lymphocytes decreased	<LLN - 500/mm ³ ; <LLN - 0.5 x 10 ⁹ /L	<500 - 200/mm ³ ; <0.5 - 0.2 x 10 ⁹ /L	<200 - 50/mm ³ ; <0.2 x 0.05 - 10 ⁹ /L	<50/mm ³ ; <0.05 x 10 ⁹ /L	-

Decreased CD4 count will have grades 1-4, with

- Grade 1 being any values from the LLN to 500/mm³,
- Grade 2 from <500 to 200/mm³ and
- Grade 3 from <200 to 50/mm³ and
- Grade 4 <50/mm³

Lab Test = Lymphocytes

CTCAE Term	Grade 1	Grade 2	Grade 3	Grade 4	Grade 5
Lymphocyte count decreased	<LLN - 800/mm ³ ; <LLN - 0.8 x 10 ⁹ /L	<800 - 500/mm ³ ; <0.8 - 0.5 x 10 ⁹ /L	<500 - 200/mm ³ ; <0.5 - 0.2 x 10 ⁹ /L	<200/mm ³ ; <0.2 x 10 ⁹ /L	Lymphocyte count decreased
Lymphocyte count increased	-	>4000/mm ³ - 20,000/mm ³	>20,000/mm ³	-	Lymphocyte count increased

Decreased Lymphocytes will have grades 1-4, with

- Grade 1 being any values from the LLN to 800/mm³,
- Grade 2 from <800 to 500/mm³ and
- Grade 3 from <500 to 200/mm³ and
- Grade 4 <200/mm³

Increase Lymphocytes will have grades 2 and 3 only, with

- Grade 2 from >4000 to 20,000/mm³ and
- Grade 3 >20,000/mm³

Lab Test = Neutrophils

CTCAE Term	Grade 1	Grade 2	Grade 3	Grade 4	Grade 5
Neutrophil count decreased	<LLN - 1500/mm ³ ; <LLN - 1.5 x 10 ⁹ /L	<1500 - 1000/mm ³ ; <1.5 - 1.0 x 10 ⁹ /L	<1000 - 500/mm ³ ; <1.0 - 0.5 x 10 ⁹ /L	<500/mm ³ ; <0.5 x 10 ⁹ /L	-

Neutrophils will have grades 1-4, with

- Grade 1 being any values from the LLN to 1500/mm³,
- Grade 2 from 1000 to <1500/mm³ and
- Grade 3 from 500 to <1000/mm³ and
- Grade 4 <500/mm³

Lab Test = Platelets

CTCAE Term	Grade 1	Grade 2	Grade 3	Grade 4	Grade 5
Platelet count decreased	<LLN - 75,000/mm ³ ; <LLN - 75.0 x 10 ⁹ /L	<75,000 - 50,000/mm ³ ; <75.0 - 50.0 x 10 ⁹ /L	<50,000 - 25,000/mm ³ ; <50.0 - 25.0 x 10 ⁹ /L	<25,000/mm ³ ; <25.0 x 10 ⁹ /L	-

Platelet count will not be CTCAE graded

Lab Test = WBC

CTCAE Term	Grade 1	Grade 2	Grade 3	Grade 4	Grade 5

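### SAP 9.5 has two grading rules that conflict with their own CTCAE rows (hypokalaemia Grade 3, triglyceride Grade 4) and leaves platelets ungraded without giving a reason

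*SAP*

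**What the plan says.** SAP 5.17.3 sends each laboratory test down one of two routes. Tests with a grade in SAP 9.5 go into a worst-grade table: "Shifts from baseline to greatest (worst) post-baseline laboratory grade will be presented". The rest follow the provision that begins "For parameters not graded as described above, laboratory values outside the normal range for each systematically collected hematology, blood chemistry, and urinalysis parameters". They are flagged low, normal or high and shifted from baseline to the minimum and maximum post-baseline value. SAP 3.2.2.1 adds a definition that works only for graded tests: "A treatment-emergent laboratory toxicity is defined as an increase of at least one toxicity grade".

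In SAP 9.5:

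- **Hypokalaemia.** The CTCAE row puts Grade 3 below 3.0 and down to 2.5 mmol/L, and Grade 4 below 2.5. The rule gives Grade 1 from the LLN to 3.0, then "Grade 3 from >2.5 to 3.0 mmol/L", then Grade 4 below 2.5.
- **Triglycerides.** The row puts Grade 4 above 1000 mg/dL, equivalently above 11.4 mmol/L. The rule says "Grade 4 from >1000 mmol/L".
- **Platelets.** The row has four numeric grades, with limits at 75, 50 and 25 × 10⁹/L. The line beneath it says "Platelet count will not be CTCAE graded".

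Protocol 2.3 states that "bone marrow suppression, impairment of spermatogenesis and on male fertility, and increased mitoses are considered potential risks" and relies partly on monitoring of blood counts to limit these risks. A platelet count below 100 × 10⁹/L is an AESI in Protocol 8.3.7 and SAP 3.2.1.1.

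**The concern.** The lists under each CTCAE row are the operative instructions for the grading program. A slip there passes straight into the worst-grade shift table. A potassium of 3.0 could be shown as Grade 3, a potassium of 2.5 could drop out, and the most extreme triglyceride results could lose their grade.

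The platelet line is a different matter, a choice rather than a slip. It removes from the graded output one of the counts most relevant to a named potential risk, and the SAP does not say why. At stake is whether the report can show from laboratory data how deep any platelet fall was, as it will for neutrophils and haemoglobin.

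**Working it through.** No sample-size, power or alpha figure enters this point.

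**1. Triglycerides.** The inputs are the paired limits in the SAP 9.5 row: 150/1.71, 300/3.42, 500/5.7 and 1000/11.4 (mg/dL over mmol/L).

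- Conversion factor: 11.4 / 1000 = 0.0114 mmol/L per mg/dL.
- Check of the row: 150 × 0.0114 = 1.71; 300 × 0.0114 = 3.42; 500 × 0.0114 = 5.70. The row is internally consistent.
- The rule's Grade 4 limit in mg/dL: 1000 / 0.0114 = 87,719. Ratio to the row's limit: 1000 / 11.4 = 87.7.
- The rule's Grade 3 stops at 1000 mg/dL. Read literally, everything above 1000 and up to 87,719 mg/dL has no grade. Grades 1 to 3 match the row.

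**2. Hypokalaemia.** The row and the rule were compared at every 0.1 mmol/L from 2.0 to 3.6. The 0.1 step and an LLN of 3.5 mmol/L are assumptions, because the documents give neither.

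| Potassium (mmol/L) | CTCAE row | SAP rule |
|---|---|---|
| 2.0 to 2.4 | Grade 4 | Grade 4 |
| 2.5 | Grade 3 | none |
| 2.6 to 2.9 | Grade 3 | Grade 3 |
| 3.0 | Grade 1 | Grade 1 and Grade 3 |
| 3.1 to 3.4 | Grade 1 | Grade 1 |

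The row and the rule disagree at two exact values. They also differ at the assumed LLN itself, because the rule starts at the LLN. That phrasing recurs across tests and is not counted here. The rules for low calcium, glucose, magnesium and sodium include the lower limit and exclude the upper one, so the potassium rule is out of line with its neighbours. The hyperkalaemia rule matches its row.

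**3. Platelets.** The printed grades are set against the outputs that SAP 5.17.3 and 3.2.1.1 would give:

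| Platelets (10⁹/L) | Grade in printed row | Low/normal/high shift | AESI criterion met |
|---|---|---|---|
| 100 to below LLN | 1 | low | no |
| 75 to below 100 | 1 | low | yes |
| 50 to below 75 | 2 | low | yes |
| 25 to below 50 | 3 | low | yes |
| below 25 | 4 | low | yes |

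Two things follow. The shift table has one category for all five bands. And the AESI limit lies inside Grade 1, so grading alone would not isolate participants below 100.

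**4. Comparison with other tests in the same appendix.**

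- The other two haematology AESI limits are neutrophils below 1.5 × 10⁹/L and haemoglobin below 10 g/dL. Both coincide with the start of Grade 2 in SAP 9.5, so the worst-grade table recovers those counts.
- Liver tests (SAP 5.17.3) and QTcF (SAP 5.17.5) get threshold counts of their own. Platelets get neither grades nor a threshold count.
- The other tests left wholly ungraded are uric acid, bicarbonate, phosphate, eosinophils and urine blood. Each has a row that depends at least partly on symptoms, intervention or baseline. The platelet row is numeric throughout.
- Screening excludes platelet counts outside the normal range (Protocol 5.2, criterion 11), so the shift table will mostly show normal to low, without depth.

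**The case against.** A reader might infer that all platelet severity information is lost, or that the toxicity tables will be wrong. The documents support neither.

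- Counts below 100 × 10⁹/L are AESIs, and SAP 5.17.1 summarises AESIs separately. Every count that would be Grade 2 to 4 meets that criterion.
- Protocol Table 13 grades adverse events, including clinically significant laboratory abnormalities, by NCI-CTCAE version 5.0, and SAP 5.17.1 tabulates events by severity.
- Ungraded tests are still shifted to their minimum value, and all data are listed. Visit summaries cover a selection of quantitative results, which may include platelets.
- Not grading platelets is an explicit decision, and the appendix makes the same decision for five other tests. It omits information. It does not make a table false.
- The triglyceride entry is plainly a unit slip, because the row above it is right. The potassium slip touches two exact values and one direction only.
- SAP 5.17.3 names no treatment-emergent toxicity table. The term is defined in 3.2.2.1, and the table shells are a separate document.

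Most of this stands, and it limits the consequence. Three things survive it. The two rules still contradict their rows. Independent programming (SAP 9.4) will not necessarily catch that, since both programmers may work from the same text. And AESI capture depends on the investigator's eCRF entry (SAP 3.2.1.1), so it does not replace a count taken from the laboratory data.

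**Conclusion.** The point holds in a limited form. There are two definite errors in SAP 9.5: the hypokalaemia Grade 3 boundary, which affects values of exactly 2.5 and 3.0 mmol/L, and the triglyceride Grade 4 unit, which affects values above 1000 mg/dL. Both matter only if the rules are programmed as written. There is also one unexplained omission. Platelets are absent from the worst-grade shift table and cannot meet the treatment-emergent laboratory toxicity definition, despite the named marrow risk and the grading of haemoglobin, neutrophils, lymphocytes and WBC.

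The size is small. A few values may be misgraded or left out, and the depth of any platelet fall will not be tabulated by grade. How many participants this touches cannot be judged from the documents. They give neither the laboratory's normal limits nor its reporting precision, and they contain no results. Efficacy, eligibility and the protocol's discontinuation criteria are unaffected.

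**What to change.** In SAP 9.5:

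1. Hypokalaemia Grade 3: 2.5 to <3.0 mmol/L. Then 2.5 is Grade 3 only and 3.0 is Grade 1 only, with no gap or overlap.
2. Triglyceride Grade 4: >1000 mg/dL (>11.4 mmol/L).
3. Platelets: grade 1 to 4 with the thresholds already printed, and include them in the worst-grade shift table. If they are to stay ungraded, state the reason.

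In SAP 5.17.3, add the number and percentage of participants per group with any post-baseline central-laboratory platelet count below 100 × 10⁹/L, since grades alone will not show it.

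The cost is a few lines in one appendix, a short addition to the grading program and one extra table row or small table. No new data are needed. If the SAP can no longer be amended, its section 6 already provides for documenting such a change in the clinical study report.

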9.6. Abbreviations

Abbreviation	Definition
ACT	Acceptance and Commitment Therapy
AE	Adverse event
AESI	Adverse events of special interest
ALP	Alkaline phosphatase
ALT	Alanine aminotransferase
APMP	Abuse Potential Monitoring Plan
AR[1]	First-order Autoregressive Structure
AST	Aspartate aminotransferase
BID	Twice daily
BLQ	Below the level of quantification
CBT	Cognitive Behavioral Therapy
CGI-S	Clinical Global Impression Severity of Symptoms Scale
CI	Confidence interval
CRF	Case report form
C-SSRS	Columbia-Suicide Severity Rating Scale
CTCAE	Common Terminology of Criteria for Adverse Events
CV%	Coefficient of variation
DSM-5-TR	Diagnostic And Statistical Manual Of Mental Disorders, Fifth Edition, Text Revision
eCFR	Electronic case report form
ECG	Electrocardiograms
EQ-5D-5L	European Quality of Life
EQ-VAS	EQ Visual Analog Scale
HAM-A	Hamilton Anxiety Rating Scale
ICE	Intercurrent event
IMP	Investigational medicinal product
IRT	Interactive Response Technology
LLN	Lower limit of normal
LLOQ	Lower limit of quantification
MAR	Missing at random
MNAR	Missing not at random
MBCT	Mindfulness Based Cognitive Therapy

Abbreviation	Definition
MedDRA	Medical Dictionary for Regulatory Activities
MINI	Mini International Neuropsychiatric Interview
MMRM	Mixed model for repeated measures
n	Number of observations
N	Number of participants
PDSS	Panic Disorder Severity Scale
PK	Pharmacokinetic
PWC	Physician Withdrawal Checklist
Q1	First quartile
Q3	Third quartile
QTcF	Corrected QT values using Fridericia's method
SAE	Serious adverse event
SDS	Sheehan Disability Scale
SE	Standard error of the mean
TEAE	Treatment-emergent adverse events
TESAE	Treatment-emergent serious adverse event
ULN	Upper limit of normal
VAS	Visual analog scale
WHO	World Health Organization
